Currently there is no guideline or consensus for the treatment of elective knee arthroscopies[2], [4]. However, when analyzing the responses of a questionnaire sent to various orthopedic units members of the “Swedish Arthroscopy Society”, it was reported that the most common anesthesia technique corresponded to 1) general (83%), 2) local anesthesia without or with minimal sedation was used in 13% of patients, 3) while spinal anesthesia was performed in 4% of patients[2]. In the postoperative period, 1/37 (2.70%) of the units interviewed did not use local intra-articular anesthesia for the treatment of pain, 8/37 (21.62%) used short-term lidocaine or prilocaine (with or without adrenaline), in 20

/37 (54.05%) used long-acting intra-articular bupivacaine, 5/37 (13.51%) used morphine and 3/37 (8.10%) NSAIDs[2].

After the use of the different anesthesia methods, the adverse effect on the articular cartilage has been evaluated, in addition to the favorable analgesia effects for pain management, showing no difference in the harmful effect between the use of general, spinal and analgesia. local[5].

The effect of the use of various analgesics on pain control in procedures similar to knee arthroscopy has previously been studied[6-10].

After arthroscopy that does not include a procedure such as anterior cruciate ligament, tibial tuberosity osteotomy, medial patellofemoral ligament or meniscus surgery, a median opioid consumption corresponding to 11.3 (0-52) pills has been reported[11].

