**Figure 1. EVisual Analogue Scale (VAS)**

### **Ropivacaine**

Ropivacaine is a long-acting amide local anesthetic that began clinical use in 1996.[20] Structurally, it is chemically similar to bupivacaine and mepivacaine, because they are derivatives of "pipecoloxylidide" (name not defined in Spanish), however, ropivacaine,

being the agent with the lowest lipophilic behavior of its peers, is characterized by lower toxicity. systemic when compared with bupivacaine and levobupivacaine[21]–[23].

The possible benefits of ropivacaine have been studied in different contexts: 1) in infiltration anesthesia[20], 2) in peripheral neural blockade (sciatic and femoral nerves)[24], [25]; 3)continuous postoperative analgesia[26]–[29]; 4) intra-articular application[30], [31].

Until now, the efficacy (comparison against placebo or non-active substance) of ropivacaine in the control of pain after knee arthroscopy has not been evaluated. However, the results of the efficacy or efficiency of active substances similar to ropivacaine have been studies [32-41]. Ropivacaine, such as bupivacaine or levobupivacaine in pain control, in different strata of the population that has undergone knee arthroscopy, as well as the adverse effects and limitations of studies previously carried out in the population of interest for this study.

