## **Objectives**

General objective:

- To evaluate the analgesic effect of the intra-articular administration of 0.75% ropivacaine in the immediate postoperative period of knee arthroscopy in acute injuries.

Specific objectives:

- To evaluate the effect of intra-articular administration of 0.75% ropivacaine in reducing opioid consumption in the immediate postoperative period of knee arthroscopy in acute injuries.
- To evaluate the effect of intra-articular administration of 7.5% ropivacaine on mobility in the immediate postoperative period of knee arthroscopy in acute injuries.

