### *Blinding:*

Blinding will be performed once the patient will agree to participate; the physician in charge of randomization will inform the anesthesiologist of the maneuver that corresponds to the patient programmed for surgery, who will prepare the dose for the patient and hands it to the physician who will apply the maneuver (who is blinded to the maneuver). All patients will receive 10 ml of solution with different doses of ropivacaine, the application vehicles being equal in physical appearance. The physician who will evaluate the outcome will not participate in the randomization, surgery or application of the maneuver, and will remain blinded to the dose the patient receives, as does the patient.

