### *Sample size*

Expecting an absolute difference, an absolute difference of 30% is expected for the presence of moderate-severe pain, considering a level of significance=5% and power=80%. Needed are 68 subjects, 34 for each arm.

Given that the evaluation of outcome is performed 2 hrs. after the application of the maneuver, and due to the low incidence of postoperative anesthetic complications, loss of information is estimated at <1%.

*Sample size and statistical analysis:* Sample size was estimated to establish a difference of 30% in considering the presence of moderate-severe pain among patients treated with different doses of ropivacaine, considering an alpha level of 0.05 and beta of 0.20. Required

were 68 patients divided into two groups of 34 each. Loss of information was expected at <1%, and 2 subjects were added to the sample size, increasing the requirement to 70 subjects in total. For statistical analysis, the statistical program SPSS version 27 will be used (IBM Armonk, New York). Contrast of the incidence of outcomes between the two groups by different doses of ropivacaine will be carried out by  $\chi^2$  or Fisher exact test, when necessary. Multivariate analyses will be performed by logistic regression analysis, considering a value of  $p < 0.05$  as significant, and double gradient differences in exposure to different variables between treatment groups were included in multivariate analysis.

In the *intention-to-treat analysis* (ITT), the main and secondary outcomes will be contrasted between the groups, considering the randomization of the different doses of ropivacaine, and in the *per-protocol analysis (PP)*, the results of the incidence of moderate-severe pain will be contrasted between groups formed by randomization; however, those that received opioids in the first 2 hours post-surgery will be excluded, in order to know the effect of the use of ropivacaine at 7.5% without the effect of a conjugate maneuver.

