#### *Variables to be evaluated*

Dependent variable	
Pain (Primary outcome)	Conceptual definition: Sensory and emotional experience associated with a present or potential injury or a described one.  Operational definition: The sensation of painful discomfort at the surgical site (Mild, moderate or severe).  Type of variable: Dichotomous qualitative.  Measuring instrument: VAS (0-10 points)  Measurement units: Mild 0-3 points, moderate-severe 4-10 points.

Opioid use	
Conceptual definition: Drug whose analgesic action is produced thanks to the interaction with the opioid receptors of the neurons of the central nervous system.
 
Operational definition: According to the VAS pain score administration of Tradol dose of 50mg IV.
 
Type of variable: Qualitative dichotomous
 
Measuring instrument: Information extracted from the patient's file.
 
Measurement units: Not use / Use.

Mobility	
Conceptual definition: Amplitude of joint oscillation within natural limits.
 
Operational definition: The active mobility performed by the patient in the postoperative period.
 
Variable type: Dichotomous qualitative.
 
Measuring instrument: Observation made by the doctor in the postoperative period after the indication of flexion and extension of the leg, elevation and descent of it actively before the doctor.
 
Measurement units: Present / absent.

Independent variable	
Ropivacaine 0.75%	
Conceptual definition: Long-lasting amide-type local anesthetic with lower lipid solubility.
 
Operational definition: IA administration to the knee of 10 ml of 0.75% ropivacaine.
 
Variable type: Dichotomous qualitative.
 
Measuring instrument: Experimental maneuver.

	Measurement units: No / Yes
Ropivacaine 0.2%	
Conceptual definition: Long-acting amide-type local anesthetic with lower lipid solubility
 
Operational definition: IA administration to the knee of 10 ml of 0.2% ropivacaine.
 
Variable type: Dichotomous qualitative.
 
Measuring instrument: Experimental maneuver.
 
Measurement units: No / Yes

Peripheral variables/covariates/Probable confounders /Probable interactors	

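### Two ropivacaine doses 3.75-fold apart are compared, but no adverse-effect outcome is defined or analysed, so any preference for a dose would rest on analgesic benefit alone

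*Combined protocol and SAP*

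**What the plan says.** **Exposure.** The Variables to be evaluated table defines the arms as "IA administration to the knee of 10 ml of 0.75% ropivacaine" and "IA administration to the knee of 10 ml of 0.2% ropivacaine". The Blinding section confirms the equal volume: "All patients will receive 10 ml of solution with different doses of ropivacaine".

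**Outcomes.** The same table lists three dependent variables: pain (primary), opioid use and mobility. The general objective is analgesic effect. The specific objectives are "To evaluate the effect of intra-articular administration of 0.75% ropivacaine in reducing opioid consumption" and the effect "on mobility in the immediate postoperative period of knee arthroscopy in acute injuries". The rest of the table holds the two treatment variables and baseline or surgical covariates.

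**Collection.** The Abstract says data go on established forms that include the study's variables of interest, and that opioid administration is recorded as well as pain. Model description sets one pain assessment, two hours after surgery, by a blinded physician.

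**Analysis.** The statistical paragraph under Sample size contrasts the main and secondary outcomes by intention to treat, and moderate-severe pain per protocol. It has no safety analysis or safety population.

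**Where harm is mentioned.**
- Background: "the adverse effect on the articular cartilage has been evaluated, in addition to the favorable analgesia effects for pain management". The sentence goes on to report no difference in harm between general, spinal and local methods.
- Ropivacaine: the drug, "being the agent with the lowest lipophilic behavior of its peers, is characterized by lower toxicity", is compared with bupivacaine and levobupivacaine.
- Sample size: "due to the low incidence of postoperative anesthetic complications, loss of information is estimated at <1" per cent.
- Exit from the study: intraoperative events that stop the surgery or prevent the injection.

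**The concern.** The trial asks how two doses of one drug compare, and its hypothesis favours the higher concentration. If 0.75% gives less pain, the next question is whether the additional 55 mg brought more adverse effects, and the plan defines no data that would answer it. Among the defined variables, an adverse effect that interfered with the flexion-extension test could show up only as a missing pain score or as absent mobility, and neither could be told apart from other causes.

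The plan also relies on anesthetic complications being uncommon when it sets its loss allowance, but does not count them, so that premise cannot be checked from the trial's own data.

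**Working it through.** **1. The plan's own sample size.** Inputs: moderate-severe pain in 37.5% against 7.5% (Abstract); alpha 0.05 and power 80% (Sample size), taken as two-sided because sidedness is not stated; chi-square or Fisher exact test. Enumerating the two-sided Fisher exact test gives power of 79.4% with 33 per arm and 81.0% with 34. So 34 is the smallest size reaching 80%, and the stated 68 is reproduced. The plan adds 2 for losses: 70 in total, or 35 per arm. The point does not depend on this calculation, which serves only to fix the number per arm used below.

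**2. Dose contrast.** A 1% solution holds 10 mg/ml.
- Higher arm: 10 ml × 7.5 mg/ml = 75 mg
- Lower arm: 10 ml × 2 mg/ml = 20 mg
- Difference: 75 − 20 = 55 mg; ratio: 75 / 20 = 3.75

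The Abstract, the mobility objective and the Sample size section also print 2% and/or 7.5%. Those entries must be reconciled with 0.2% and 0.75%. The ratio is 3.75 in either notation (7.5 / 2 = 0.75 / 0.2), but the milligram figures rest on the arm definitions in the variables table.

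**3. Is there a harm outcome?**
- Objectives: pain, opioid use, mobility.
- Dependent variables: the same three.
- Covariates: none is an adverse event or complication.
- Analysis: no safety table or population.
- Exit events: the Maneuver section places the injection after the portals are sutured. An event that stops surgery or prevents the injection therefore comes before exposure.

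No adverse-effect outcome, collection method or analysis appears in the supplied text.

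**4. What an added outcome could show.** The documents give no adverse-event rates, so those below are assumptions.

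Upper limit after zero events in n patients: one-sided 95% is 1 − 0.05^(1/n); two-sided 95% is 1 − 0.025^(1/n). Chance of at least one event in an arm at true rate p: 1 − (1 − p)^n.

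| | n = 34 | n = 35 |
|---|---|---|
| Zero events, one-sided limit | 8.4% | 8.2% |
| Zero events, two-sided limit | 10.3% | 10.0% |
| At least one event, p = 1% | 28.9% | 29.7% |
| p = 2% | 49.7% | 50.7% |
| p = 5% | 82.5% | 83.4% |
| p = 10% | 97.2% | 97.5% |

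Fisher exact power for a between-arm difference with 35 per arm is about 3% for 5% against 10%, 14% for 5% against 15%, and 33% for 5% against 20%.

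**The case against.** Several stronger readings are tempting, and the documents do not support them.

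- *Nothing at all is recorded about harm.* The forms are not in the supplied text, consent pages were removed, and routine chart entries may exist. What can be said is that no harm outcome is defined or analysed.
- *Every outcome measures benefit only.* The Justification describes opioids as a risk to patients, so opioid use bears on harm. Mobility could worsen as well as improve. Even so, neither variable identifies an adverse effect of the injection.
- *The protocol itself warns of dose-related harm.* The Background sentence on cartilage ends in reassurance and compares anesthesia methods. The Ropivacaine section compares drugs. Neither addresses 0.2% against 0.75%. The hepatic and allergy exclusions come without a stated reason, and the cartilage grades define the population.
- *The trial will recommend the higher dose.* No section commits to a recommendation. The risk lies in how a favourable pain result would be used.

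The strongest remaining argument is precision. The plan expects complications to be uncommon, so rates of 1% or 2% matter at least as much as 5% or 10%. At those low rates, an arm of 34 has only about a 29% or 50% chance of showing a single event. No table of this size could establish what the additional dose costs unless harms were frequent and very different between arms. This stands, and it limits the remedy to description. It does not remove the case for recording, because common effects would probably be seen.

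A second fair objection is that reading the patient's file could unblind the pain assessor. The documents do not say whether the file shows the dose, so the fix has to guard against this.

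**Conclusion.** The point holds as a defined omission: a 75 mg against 20 mg comparison (3.75-fold) with no planned adverse-effect outcome and no safety analysis. Followed as written, the plan yields no planned comparison of harm by arm, and a preference for either dose would rest on analgesic benefit alone. The primary comparison and the sample size are sound in this respect and need no change.

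The gain from correcting it is modest. It would give a count per arm that could exclude only fairly common early effects, with an upper limit of 8.4% one-sided or 10.3% two-sided after zero events in 34. The detection figures rest on assumed event rates. The finding covers the objectives, methods, variables and analysis text supplied, not the unseen forms. This is a cheap improvement, not a flaw that undermines the trial.

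**What to change.** 1. Add a secondary outcome to the Variables to be evaluated table: any adverse effect from the injection to the 2-hour assessment, recorded as yes/no with type, time and severity.
2. Have the blinded evaluator ask about it at the existing assessment, after the VAS score is written down, so that the question cannot influence the pain rating.
3. If the patient's file is also used, have existing study staff other than that evaluator extract it, or extract it only once the VAS is locked. This keeps the blinding that the Blinding section requires.
4. In the analysis paragraph, specify a descriptive table by assigned arm with exact confidence intervals and no significance claim.
5. State that later effects, including those on cartilage, are outside what the trial can show.

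The cost is one block on the form, one table and a few minutes per patient, with no added visit, staff or participants. The drawback is the limited precision shown above.
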